5. INTRODUCTION

5.1. Background and Rationale

[figure not shown]
5.1.1. Background on Motor Fluctuations in Parkinson's Disease Patients

Levodopa (LD) remains the “standard of care” for the management of motor symptoms for Parkinson's disease (PD) patients. However, long-term treatment with LD is complicated by the development of motor fluctuations, also referred to as hypomobility or OFF episodes. The development of OFF episodes relates to both pharmacokinetic (PK) and pharmacodynamic factors. Over time, patients frequently experience a progressive shortening of the duration of LD clinical effect, leaving patients vulnerable to episodic OFF episodes which may be disabling. It is estimated that up to half of LD-treated PD patients develop such motor fluctuations within 5 years ([Parkinson Study Group 1996](#), [LeWitt 2008](#), [Stocchi 2010](#)).

Following oral ingestion, LD is absorbed through an active transport mechanism that is specific for large neutral L-amino acids in the proximal small intestine. The absorption of LD is subject to considerable inter- and intra-patient variability and is affected significantly by alterations in gastrointestinal (GI) motility and food intake. Frequently, poor absorption following administration of a standard oral LD dose results in sub-therapeutic levels, leaving patients susceptible to the development of OFF episodes ([Baruzzi 1987](#), [Pfeiffer 1996](#), [Olanow 2006](#)).

Treatment options for patients with motor response fluctuations are limited. Various strategies may be employed to enhance the clinical effectiveness of central dopaminergic stimulation to reduce the frequency of motor fluctuations, including the use of dopamine agonists, catechol-O-methyltransferase (COMT) inhibitors, extended-release oral LD formulations, or modified dosage of their standard oral LD preparations ([LeWitt 2008](#), [Olanow 2009](#)).

Management of OFF episodes is done frequently through adjustment of the inter-dose interval of standard oral LD preparations or through administration of unscheduled partial or full doses of oral LD-containing products. However, following treatment with oral LD preparations, resumption of motor function is unreliable owing to the challenges in GI transit and LD absorption ([Ondo 2010](#)), and the development of intermittent OFF episodes remains a significant issue despite attempts to manage patients using oral LD agents alone.

 CVT-301 (LD inhalation powder) is being developed for the treatment of episodic motor fluctuations (OFF episodes) in patients with PD, as an adjunct, as needed (PRN) therapy to provide relief from intermittent motor fluctuations (OFF episodes) that affect many PD patients.

5.1.2. Background on CVT-301 (Levodopa Inhalation Powder)

CVT-301 is a dry powder LD formulation (levodopa inhalation powder [LIP]) designed for inhaled delivery using a proprietary delivery system. Using this technology, a variety of medications have been administered previously to humans, including proteins (e.g., insulin, human growth hormone) and small molecules (e.g., epinephrine, tropium) ([Rave 2007](#),

[Chipman 2005](#), [Walvoord 2009](#), [Dewey 2001](#), [Dunbar 2004](#), [Oleson 2010](#)). This delivery system is capable of delivering therapeutics with high efficiency over a range of inspiratory flow rates using a passive, breath-actuated device ([DeLong 2005](#)).

CVT-301 is being developed as treatment for episodic motor fluctuations (OFF episodes) in patients with PD. CVT-301 will be used as an adjunct to the patient's existing decarboxylase inhibitor (i.e., carbidopa [CD] or benserazide)-inclusive PD medication regimen.

[figure not shown]
In nonclinical studies, CVT-301 pulmonary delivery was associated with rapid LD absorption, and was associated with a shorter and less variable time to maximal drug concentration (tmax) and less variable maximal plasma concentration (Cmax) compared to oral LD administration. These PK attributes translated to pharmacodynamic advantages in a nonclinical model of PD ([Bartus 2004](#)).

[REDACTED]

[REDACTED]

[REDACTED]

[REDACTED]

5.2. Rationale

Attainment of therapeutic plasma concentrations and restoration of motor function following administration of oral LD to PD patients is variable, unreliable, and frequently delayed, not uncommonly requiring 1 hour or more to attain therapeutic responses.

The more rapid LD absorption following inhaled CVT-301 administration is expected to translate to rapid alleviation of motor OFF symptoms in patients experiencing OFF episodes.

This 12-month study will employ a randomized open-label methodology to investigate the safety and effects of CVT-301 (50 mg LD FPD) and will include a concurrent observational cohort of PD patients who will not receive study medication, but will continue to take their usual PD medications. Patients must be CVT-301-naïve, however, any patients that were enrolled from the CVT-301-002 and CVT-301-003 studies under the previous version of this protocol will be allowed to continue in the study. Patients will be randomized in a 2:1 ratio to the CVT-301 treatment group (50 mg LD FPD) or the observational cohort.

During the 12-month treatment period, patients in the CVT-301 treatment group will self-administer an inhaled study drug dose as needed when they experience OFF episodes; study medication may be used up to 5 times daily. Every day during the treatment period, the CVT-301 patients will record the following information in the Inhaled Dosing Log: the number of times the inhaler was used and the number of capsules used for each inhalation treatment. Patients in each group will continue their standard PD medications, which may be modified during the study if needed. Patients in each group will be required to attend the screening visits (Screening Visit 1 [SV1] and Screening Visit 2 [SV2]) and the 6 in-clinic treatment/observational visits (Treatment Visit/Observational Visit 1 [TV/OV1], Treatment Visit/Observational Visit 2 [TV/OV2], Treatment Visit/Observational Visit 3 [TV/OV3], and Treatment Visit/Observational Visit 4 [TV/OV4], Treatment Visit/Observational Visit 5 [TVOV5], and Treatment Visit/Observational Visit 6 [TV/OV6]). For the patients in the CVT-301 treatment group, these visits will be treatment visits and for the observational cohort, these visits will be observational visits.

CVT-301-treated patients will be followed in the clinic for the following efficacy measures: serial assessments of UPDRS Part 3 motor score following treatment in the clinic, the occurrence and severity of dyskinesia following treatment in the clinic, the occurrence of ON states during the post-treatment period, the 39-Item Parkinson's Disease Questionnaire (PDQ-39), the Patient Global Impression of Change (PGI-C) rating scale, the Schwab and England (S&E) Activities of Daily Living (ADL) score; UPDRS Part 2 score, and UPDRS Part 4 (Questions 32-35 and 36-39) score. In addition, the total daily ON time without dyskinesia, total daily ON time with troublesome dyskinesia, total daily ON time with non-troublesome dyskinesia, and total daily OFF time will be evaluated in the CVT-301-treated patients based on the PD Diary, which will be completed for the 3 consecutive days prior to SV2, TV/OV1, TV/OV2, TV/OV3, TV/OV4, TV/OV5, and TV/OV6.

All patients, regardless of treatment assignment, will undergo the safety assessments. Patient safety will be evaluated using adverse event (AE) reports, physical examination, vital signs (blood pressure [BP], heart rate [HR], and respiratory rate [RR]), clinical laboratory tests, 12-lead electrocardiograms (ECGs), spirometry, carbon monoxide diffusing capacity (DLco) maneuver, the Parkinson's Disease Impulsive-Compulsive Disorders Questionnaire (QUIP), the Epworth Sleepiness Scale, and the Columbia-Suicide Severity Rating Scale (C-SSRS).

The use of a randomized observational cohort in this study is to permit long-term contemporaneous temporal comparison to CVT-301-treated patients to describe any potential effects of CVT-301 with respect to lung function measurements. These control patients, who are eligible to use any approved treatments to manage their PD motor symptoms, represent a randomized study population that remains naïve to inhalation treatment (to avoid potential confounding interpretation of lung function data) for their PD which is required to ascertain the underlying variability in spirometry and DLco endpoints. Only a limited number of efficacy assessments will be evaluated in the patients randomized to the observational cohort. Selected efficacy measures to assess effects of CVT-301 will be evaluated in the open-label CVT-301-treated patients who use CVT-301 inhalation as a treatment of OFF symptoms.

5.2.1. Rationale for Selection of Dose

Because CVT-301 contains LD only (i.e., with no DDI), study drug will be administered only to patients taking a DDI-containing LD formulation (e.g., CD or benserazide). The study is designed to evaluate the safety and effect of adjunctive therapy (CVT-301 plus usual prescribed standard PD medication regimen). All patients, regardless of treatment assignment, will continue with their usual prescribed standard PD medication regimen for the study duration.

The dose level being studied has been observed to be clinically effective, safe, and tolerated in healthy adult volunteers as well as in PD patients in 2 completed CVT-301 clinical studies. [REDACTED]

The PK data from the selected CVT-301 dose level (50 mg LD FPD) has been well-characterized from healthy adult volunteers in [REDACTED]

CVT-301 (Levodopa Inhalation Powder)

[REDACTED]

[REDACTED]

[REDACTED]

[REDACTED]

[figure not shown]
[REDACTED]

[REDACTED]

[REDACTED]

[REDACTED]

[REDACTED]

The dose level of 50 mg LD FPD was selected for further evaluation in this study.

6. STUDY OBJECTIVES

Primary Objective

- To characterize the pulmonary safety, as assessed by spirometry (forced expiratory volume in 1 second [FEV1], forced vital capacity [FVC], and FEV1/ FVC ratio), over a 12-month period within the CVT-301-treated patients.

Secondary Objectives

- To characterize the pulmonary safety, as assessed by spirometry (FEV1, FVC, and FEV1/FVC ratio), over a 12-month period in the observational ('standard of care') cohort.
- To estimate the difference between the CVT-301-patients and the observational cohort on measures of pulmonary safety.
- To characterize the effects of CVT-301 on safety over a 12-month period: safety will be assessed by AE reports, physical examination, standard and orthostatic vital signs (BP, HR, and RR), clinical laboratory tests, 12-lead ECGs, QUIP, the Epworth Sleepiness Scale, and the C-SSRS.
- To evaluate the effect of CVT-301 on mean change from baseline in the UPDRS Part 4 measures of motor fluctuations (dyskinesias [Q32-35] and wearing off [Q36-39]) measured pre-dose at 6 and 12 months after the initiation of CVT-301 treatment.
- To characterize the occurrence and severity of examiner-rated dyskinesia following treatment of patients experiencing an OFF episode in the clinic over a 12-month period.
- To describe the effects of CVT-301 on DLco over a 12-month period.

Exploratory Efficacy Objectives

- Change from pre-dose in UPDRS Part 3 motor score at 10, 20, 30, and 60 minutes following treatment of patients experiencing an OFF episode.
- Time curves of the UPDRS response at 10, 20, 30 and 60 minutes will be evaluated descriptively

- Change from pre-dose in UPDRS Part 3 motor score at 10 to 60 minutes following treatment of patients experiencing an OFF episode.
- Proportion of patients with a ≥ 3 , ≥ 6 , and ≥ 11 -point reduction in the UPDRS Part 3 motor score from pre-dose to post-dose, at 10 to 60 minutes.
- Proportion of patients achieving resolution of an OFF to an ON state within 60 minutes after study drug is administered in the clinic, maintaining the ON state at 60 minutes after study drug administration (per the examiner's subjective assessment).
- Patient-reported total daily OFF time, total daily ON time without dyskinesia, total daily ON time with non-troublesome dyskinesia, and total daily ON time with troublesome dyskinesia, assessed by the patient and recorded in the patient diary.
- Change from baseline visit in the 39-Item Parkinson's Disease Questionnaire (PDQ-39).
- Proportion of patients who improved based on the Patient Global Impression of Change (PGI-C) rating scale measured pre-dose.
- Change from baseline visit in the Schwab and England (S&E) Activities of Daily Living (ADL) score.
- Change from baseline visit in the UPDRS Part 2 score.

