2. SYNOPSIS

Title of Study:	A Phase 3, Randomized Study Investigating the Safety of CVT-301 (Levodopa Inhalation Powder) in Parkinson’s Disease Patients With Motor Response Fluctuations (OFF Phenomena) Compared to an Observational Cohort Control
Protocol Number:	CVT-301-005
Investigators/Study Sites:	This study will be conducted at approximately 100 sites in Europe and the United States.
Phase of Development:	3
Objectives:	
Primary Objective
 
 To characterize the pulmonary safety, as assessed by spirometry (forced expiratory volume in 1 second [FEV1], forced vital capacity [FVC], and FEV1/ FVC ratio), over a 12-month period within the CVT-301-treated patients. 
Secondary Objectives
 
 To characterize the pulmonary safety, as assessed by spirometry (FEV1, FVC, and FEV1/FVC ratio), over a 12-month period in the observational (‘standard of care’) cohort. To estimate the difference between the CVT-301-treated patients and the observational cohort on measures of pulmonary safety. To characterize the effects of CVT-301 on safety over a 12-month period: safety will be assessed by adverse event (AE) reports, physical examination, standard and orthostatic vital signs (blood pressure [BP], heart rate [HR], and respiratory rate [RR]), clinical laboratory tests, 12-lead electrocardiograms (ECGs), the Parkinson’s Disease Impulsive-Compulsive Disorders Questionnaire (QUIP), the Epworth Sleepiness Scale, and the Columbia-Suicide Severity Rating Scale (C-SSRS). To evaluate the effect of CVT-301 on mean change from baseline in the UPDRS Part 4 measures of motor fluctuations (dyskinesias [Q32-35] and wearing off [Q36-39]) measured pre-dose at 6 and 12 months after the initiation of CVT-301 treatment. To characterize the occurrence and severity of examiner-rated dyskinesia following treatment of patients experiencing an OFF episode in the clinic over a 12-month period To describe the effects of CVT-301 on DLco over a 12-month period.

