12.1. Determination of Sample Size

Approximately 250 CVT-301 treatment patients and 115 control patients will be enrolled in this study. It is assumed that the drop-out rate will be approximately 25%.

Assuming that there is no difference in the changes from baseline between the CVT-301-treated patients and the observational cohort in regards to FEV1, the study has the following power for the comparison between the 2 groups. The upper limit of the 95% confidence interval for the difference between the 2 groups in change from baseline in FEV1 will be less than 0.121 L with 90% power, assuming 188 and 86 patients completing the study in the CVT-301 treatment group and observational cohort, respectively.

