12.6. Exploratory Efficacy Analysis

The derivation of the exploratory efficacy variables will be defined in detail in the SAP.

The changes from baseline in continuous exploratory efficacy variables will be estimated using an MMRM. The model will include visit and the stratification variables (Hoehn and Yahr stage and screening FEV1 and/or FEV1/FVC) as fixed factors. The baseline value will be used as a covariate. For variables which do not have a pre-treatment baseline assessment, OFF-state baseline UPDRS Part 3 score will be used as the baseline covariate. An unstructured covariance structure will be applied for the MMRM. In case the model will not converge with the unstructured covariance structure, compound symmetry will be used instead.

The sensitivity analyses will be specified in the SAP. Sensitivity analysis will be performed at least for the method to handle missing data (e.g., last observation carried forward, pattern mixture model using multiple imputation instead of MMRM), definition of analysis population (e.g., patients completing the study instead of observed cases), and statistical method (e.g., analysis of covariance [ANCOVA] models separately for each visit instead of MMRM).

The categorical data will be primarily evaluated descriptively. Each visit will be evaluated separately for the categorical endpoints.

The exploratory efficacy data collected from the patients in the observational cohort will be summarized with descriptive statistics.

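### The primary objective is the uncontrolled FEV1 change within CVT-301 patients, while the randomized control and the only power statement serve a between-group difference that is ranked secondary.

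*Protocol*

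**What the plan says.** The title in the protocol synopsis presents the study as a randomized safety study of CVT-301 "Compared to an Observational Cohort Control". Section 5.2 explains the control arm: "The use of a randomized observational cohort in this study is to permit long-term contemporaneous temporal comparison to CVT-301-treated patients", so that effects on lung function can be described. It adds that these patients stay free of inhaled PD treatment so that lung function data are not confounded.

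Section 6, repeated in the synopsis, makes the primary objective the characterization of FEV1, FVC and their ratio "over a 12-month period within the CVT-301-treated patients". Among the secondary objectives is "To estimate the difference between the CVT-301-patients and the observational cohort on measures of pulmonary safety".

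Section 12.1 sizes the study. It says that "the study has the following power for the comparison between the 2 groups", starting from this premise: "Assuming that there is no difference in the changes from baseline between the CVT-301-treated patients and the observational cohort in regards to FEV1". The upper 95% confidence limit for the difference in "change from baseline in FEV1 will be less than 0.121 L with 90% power", with 188 and 86 completers. It gives no SD, and no precision or power for the within-arm objective.

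Section 12.5 plans to estimate both the spirometry changes and the group difference with a mixed model for repeated measurements. Under Section 9.2.1, patients who completed CVT-301-002 or CVT-301-003 are assigned only to CVT-301.

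**The concern.** The protocol randomizes a concurrent control to interpret lung function and sizes the study on the contrast with it, then gives first rank to a quantity that does not use the control. A 12-month change within one arm is the sum of any drug effect and whatever would have happened anyway: ageing, change in the disease, and learning or fatigue with repeated spirometry. Read as the main result, a decline could be taken for harm when it is background, and practice gains could hide real harm. The controlled difference removes what is common to both arms, but it stands second. The ranking of objectives is fixed by the protocol itself and is not detail that is normally deferred to an SAP.

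**Working it through.** **Inputs.** From Section 12.1: bound 0.121 L, power 90%, true difference 0, completers 188 and 86, enrolment 250 and 115, dropout 25%. From Section 7: 2:1 allocation. Not in the protocol, hence assumed: the SD of FEV1 change, and the background decline.

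**1. Completers.** 250 × 0.75 = 187.5 and 115 × 0.75 = 86.25, which match 188 and 86.

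**2. The plan's power figure.** The 90% cannot be reproduced without an SD, so the SD is solved for. With f = √(1/188 + 1/86) = 0.1302 and a two-sided 95% limit,

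SD = 0.121 / [(1.960 + 1.282) × 0.1302] = 0.287 L.

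A t-based version gives 0.286 L. If the limit is read as one-sided 95%, SD = 0.121 / [(1.645 + 1.282) × 0.1302] = 0.318 L.

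**3. Precision of the two estimates at SD 0.287 L.**
- Within CVT-301: 1.96 × 0.287 / √188 = 0.041 L.
- CVT-301 against observational: 1.96 × 0.287 × 0.1302 = 0.073 L.

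| SD (L) | Within-arm half-width (L) | Between-group half-width (L) |
|---|---|---|
| 0.25 | 0.036 | 0.064 |
| 0.287 | 0.041 | 0.073 |
| 0.318 | 0.045 | 0.081 |
| 0.35 | 0.050 | 0.089 |

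These are simple two-sample figures. A model adjusting for baseline may do somewhat better.

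**4. What background change alone does to the within-arm interval.** Suppose there is no drug effect and background decline is d over the year. The standard error is 0.287/√188 = 0.0209 L, and the chance that the 95% interval lies wholly below zero is Φ(d/0.0209 − 1.96).

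| Assumed d (L a year) | Chance that the interval excludes zero on the harm side |
|---|---|
| 0.02 | 16% |
| 0.04 | 48% |
| 0.06 | 82% |

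The expected interval excludes zero once d exceeds about 0.041 L. In the between-group difference, a d common to both arms cancels.

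**5. Effect of removing roll-over patients.** The protocol does not give their number. As an illustration only: strict 2:1 allocation with 115 controls gives 230 randomized to CVT-301, against 250 planned. Then 230 × 0.75 = 172.5, say 173 completers. The root becomes √(1/173 + 1/86) = 0.1319, the half-width 1.96 × 0.287 × 0.1319 = 0.074 L, and the power at 0.121 L is Φ(0.121 / (0.287 × 0.1319) − 1.96) = 89%.

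**The case against.** The strongest reply is that little is lost. The between-group difference is a stated objective, carries the only power statement and has a planned model, so both estimates will be produced. The primary objective says characterize, which does not attribute change to the drug, and no hypothesis test or alpha hierarchy is stated for the pulmonary objectives. Section 5.2 also gives the cohort a descriptive purpose, to show underlying variability. This stands as a limit on severity: the trial as a whole can address a drug effect. It does not explain why the ranking runs against the title, the rationale and the sample size.

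The contrast does not remove everything either. Section 9.4.2 bars as-needed oral levodopa and caps the daily levodopa dose during the study for CVT-301 patients only, so changes in the PD regimen may differ by arm. The case here therefore rests on ageing, disease change and test learning.

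A reader might also infer that the spirometry model lacks a group or group-by-visit term, because Section 12.6 says "The model will include visit and the stratification variables" and names only a baseline covariate besides. The documents do not support that. Section 12.5 says the group difference will be estimated and calls the model only similar. The Section 12.6 list is written for exploratory efficacy variables, which are merely summarized descriptively in the observational cohort. Section 12 leaves technical detail to the SAP. Nor would a missing interaction bear on what a within-arm objective can isolate.

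Nor is the time point really open: Section 12.1 counts patients who complete the study, which points to month 12.

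**Conclusion.** The mismatch is real and plain from the text: the quantity ranked first is the one that cannot separate a drug effect from change over time, and it has no stated precision. The controlled difference, for which the study was sized, ranks below it.

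The size of the problem depends on assumptions. At the implied SD of about 0.287 L, background decline gives an expected within-arm interval excluding zero only above about 0.041 L a year; over SDs of 0.25 to 0.35 L that threshold runs from 0.036 to 0.050 L. It would be too strong to say that background decline will look conclusive: at 0.02 L a year the chance is about 16%. It would also be too strong to say that the trial cannot isolate a drug effect, since the controlled estimate is planned. The point is one of ranking and is worth correcting because the remedy is mostly wording.

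**What to change.** - In the synopsis and Section 6, make the CVT-301 minus observational difference in FEV1 change from baseline at month 12 (TV/OV6), among randomized patients only, the primary or co-primary estimate. Keep the within-arm change as its companion summary.
- Exclude roll-over patients from CVT-301-002 and CVT-301-003 from this contrast, since they had no chance of assignment to the cohort. They can remain in the within-arm summary.
- In Section 12.1, tie the 0.121 L statement to this contrast, give the SD behind it, and state the direction of subtraction: with CVT-301 minus observational change, harm is negative and the matching statement is a lower limit above −0.121 L. Restate the power if fewer than 188 randomized CVT-301 completers are expected.

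**Cost.** Wording in the synopsis and Sections 6 and 12.1, and possibly a revised power figure. No new data are needed, and no stated test or alpha is affected. The main interval is wider, with a half-width of about 0.073 L instead of 0.041 L, and slightly wider again without roll-over patients (0.074 L in the illustration above).
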